7.2 PHARMACODYNAMIC ANALYSIS OF RESULTS

As an estimator of agalsidase beta biological activity, blood samples will be drawn to determine the variation in the agalsidase beta enzyme activity of the end-of-infusion sample (5 h) compared to baseline activity (pre-infusion).

Ratio of activity variation in both groups to be close to the unit and that the 90% CI is within the range 0.8 to 1.25 will be taken as bioequivalence criterion.

8 IMMUNOGENICITY ANALYSIS

The incidence of anti-agalsidase beta antibodies will be determined both at the start of treatment, at the end of visit II and 31 days after the end of the infusion, for both treatment groups.

Serum samples will be incubated with 1 ng agalsidase beta for 15 minutes at room temperature. Then, the enzyme activity for the samples will be determined using the 4-MU-Gal substrate.

The inhibition percentage of the samples will be determined by comparing the activity value of 1 ng agalsidase beta with the treated samples. Those samples with percentage inhibition > 50% will be reported as positive.

9 SAFETY ANALYSIS

9.1 ADVERSE EVENTS

All adverse events that occurred in the subjects during their participation in the study will be recorded. The record will be documented in the subject's Medical Record and on the applicable pages of the Case Report Form.

All solicited and unsolicited reported adverse events, regardless of treatment group or presumed causal relationship to the investigational product(s), will be reported as described in the following sections.

For all adverse events, the investigator must search and obtain adequate information, both to determine the outcome of the adverse event, and to assess whether or not it meets the criteria for its classification as a serious adverse event, which require immediate reporting to the ANMAT. For all adverse events, the investigator must obtain sufficient information to determine the adverse event causality. The investigator is required to assess such causality. For adverse events with a causal relationship to the investigational product, follow-up is required by the investigator until the event or its sequelae resolve or stabilize at a level acceptable to the investigator.

9.2 ADVERSE EVENT REPORTING

All adverse events detected by the investigator or his collaborators, or reported spontaneously by the subjects at each visit, must be reported in a special section in the Case Report Form. Adverse events will be described preferably using WHO terminology.

The study monitor will check the completion in the CRF.

The following information must be recorded for each adverse event, whether it is related to the study drug or not:

- description of the adverse event
- start date / end date
- duration of the event
- characteristics of the event (severity, expectedness, seriousness)
- action taken (report any required treatment or dose adjustments in the CRF)
- progress
- relationship to study drug (causality)

All adverse events must be documented and followed until their resolution or adequate justification, even when the subject has completed the study. Any change in the dose of the drug administered will be reported on the Case Report Form.

All non-serious adverse events (expected and unexpected) will be described in the final study report.

The Serious Adverse Event report will be prepared in compliance with ANMAT 6677/2010 provision (Section B, item 7).

The investigators will report Serious Adverse Events (SAE) immediately, within 24 hours, to the sponsor by [contact]/ [contact] (Biosidus Development Department) and/or email [contact], except those events that the protocol identifies as not requiring immediate reporting.

According to provision 6677/2010, item 7.1, the Sponsor must inform ANMAT of all Serious and Unexpected Adverse Drug Reactions (*RAMSI* – by its Spanish acronym) related to the product under study within 10 administrative business days of becoming aware of it. The RAMSI caused by a comparator product already registered in ANMAT for being marketed in the country or those related to placebo must be reported only to the ANMAT Pharmacovigilance System. The Investigator must report Serious and Unexpected Adverse Events to the Teaching and Research and Ethics Committee(s) in accordance with their requirements, in a timely manner.

Based on provision 6677/2010, item 7.3, RAMSI reporting must include the following information:

- name of the adverse reaction;
- investigational product: code, INN name and/or trade name;
- type of report: initial, update (update number) or final;
- sponsor name;
- investigational site and investigator name;
- number of ANMAT Provision authorizing the study;
- study name or title;
- participant code, age and sex;
- dates of RAMSI occurrence, investigator's report and date it is received by the sponsor;
- RAMSI seriousness criterion;
- brief description for the RAMSI;
- investigational product information: daily dose, route of administration, start and stop dates, duration of therapy, and indication;
- specify if the reaction went away when treatment was discontinued;
- specify if the reaction reoccurred with treatment rechallenge;
- concomitant medications: dosage and start and end dates;
- Participant history relevant to the RAMSI.

A single RAMSI Report per drug will be accepted, referring to all files and approval provisions by A.N.M.A.T. of studies that are being conducted in the country with that drug.

The Sponsor must immediately notify the Investigator(s) and the Ethics Committee at DIM CLINICA PRIVADA site that approved the study of all Adverse Drug Reactions that are both Serious and Unexpected that occur in other national investigational sites.

The Sponsor must inform the Investigator(s) and the Ethics Committee at DIM CLINICA PRIVADA that approved the study of all other relevant information regarding the research

product within a period not exceeding 10 business days from receiving initial information by the Sponsor.

Adverse Reactions attributable to placebo or to the comparator will not be subject to this individualized reporting system. Reports submitted to ANMAT will comply with the item 7.1, provision 6677/2010.

According to section E: Glossary, provision 6677/2010 establishes the following definitions of Adverse Drug Reaction (ADR) and Serious and Unexpected Adverse Drug Reaction (RAMSI).

Adverse Drug Reaction (ADR): noxious and unintentional response to a medicinal product related to any dose. In clinical experience prior to the approval of a new medicinal product or its new uses, particularly when the therapeutic dose cannot be established, an adverse drug reaction should be considered any reaction that involves a causal relationship between a medicinal product and an adverse event such as a reasonable possibility, that means, that the relationship cannot be ruled out.

Serious and Unexpected Adverse Drug Reaction (RAMSI): is the adverse reaction that results in death, is life threatening, requires hospitalization or prolongs an existing hospitalization or produces persistent or significant disability or incapacity, and their nature or severity is not consistent with the product information described in the IB or other documentation.

9.3 ADVERSE EVENT DEFINITION

An adverse event is any adverse medical event, occurring in a clinical research subject who has been administered a product or who uses a medical device. The event does not necessarily have to have a causal relationship with the treatment or use.

Examples of adverse events include, but are not limited to, the following:

- Abnormal findings in investigations.
- Clinically significant symptoms and signs;
- Changes in physical examination findings;
- Hypersensitivity;
- Progression/worsening of an underlying disease;

Additionally, they may include signs and symptoms resulting from:

- Drug overdose;
- Drug withdrawal;
- Drug abuse;
- Inappropriate drug use;

- Drug interactions;
- Drug dependency;
- Extravasation

9.4 ABNORMAL FINDINGS IN THE INVESTIGATIONS

Criteria for determining whether an abnormal finding on investigations should be reported as an adverse event are as follows:

- The result of the investigations is associated with accompanying symptoms, and/or
- The test result requires additional diagnostic testing and/or medical/surgical intervention, and/or
- The investigator considers the test result as an adverse event.
- A repeated abnormal investigation, in the absence of any of the conditions mentioned above, does not constitute an adverse event. Any result of an abnormal investigation determined as an error does not require being reported as an adverse event.

9.5 SERIOUS ADVERSE EVENT

A serious adverse event is any unfavorable medical event that at any dose:

- results in death;
- is life-threatening; (immediate risk of death)
- requires subject hospitalization or prolongation of existing hospitalization;
- results in a persistent or significant disability/incapacity;
- results in a congenital abnormality/birth defect.
- Important / significant medical events.

In determining whether an event is a significant medical event, medical and scientific judgment must be exercised. An important medical event may not be immediately life-threatening and/or result in death or hospitalization. However, if it is determined that the event may jeopardize the subject and require intervention to prevent one of the other outcomes listed in the definition above, the important medical event should be reported as serious.

Examples of such events are: intensive treatments in an emergency room or at home for allergic bronchospasms; blood dyscrasias or seizures that do not result in hospitalization; or the development of drug dependence or abuse

9.6 HOSPITALIZATION

Reported adverse events from clinical trials associated with hospitalizations, or prolongation of hospitalizations, are considered serious. Any initial admission (even for less than 24 hours) to a health care institution meets such criteria. Admission also includes transfer within the hospital to an acute/intensive care unit (e.g., from a psychiatric ward to a clinical ward, clinical ward to coronary unit, neurology ward, etc.).

Hospitalizations do not include the following:

- rehabilitation institutions;
- hospices;
- qualified nursing facilities;
- nursing sites;
- routine admission to an emergency room;
- same-day surgeries (outpatient/same day procedures).
- any hospitalization or prolongation of an existing hospitalization, in the absence of a clinical adverse event that precipitates it, does not constitute, in itself, a Serious Adverse Event. Examples include the following:
 - admission for treatment of a pre-existing condition, not associated with the development of a new adverse event, or with the worsening of a pre-existing condition (for example, to treat a persistent laboratory abnormality prior to treatment);
 - admission for social reasons (for example, the subject has nowhere to sleep);
 - administrative admission (for example, for an annual physical examination);
 - protocol-specified admission during a clinical trial (eg, for a procedure required by the trial protocol);
 - optional admission not associated with a precipitating adverse event (for example, for elective cosmetic surgery);
 - previously planned surgical treatments or procedures must be recorded in the baseline documentation for the entire protocol and/or for the individual subject.
 - non-invasive and invasive diagnostic and therapeutic procedures, such as surgery, should not be reported as adverse events. However, the medical condition for which the procedure is performed must be reported, if it meets the definition of an adverse event. For example, acute appendicitis beginning during the adverse event reporting period should be reported as an adverse event, and the resulting appendectomy recorded as treatment of the adverse event.

9.7 SEVERITY ASSESSMENT

If required by the adverse event case report forms, the investigator will use the adjectives MILD, MODERATE, or SEVERE to describe the maximum intensity of the adverse event. For purposes of consistency of information, these degrees of intensity are defined as follows:

MILD	Does not interfere with the subject's usual activities
MODERATE	Somehow interferes with the subject's usual activities
SEVERITY	Significantly interferes with the subject's usual activities

Please note the differentiation between severity and seriousness of an adverse event. A severe event is not necessarily a serious event. For example, a headache may be severe (significantly interferes with the performance of the subject's usual functions), but would not be classified as serious, unless it meets one of the criteria considered for serious adverse events, detailed above.

9.8 CAUSALITY ASSESSMENT (RELATIONSHIP TO MEDICATION, RELATEDNESS)

The investigator's causality assessment must be provided for all Adverse Events (serious and non-serious). The investigator's causality assessment consists of determining whether or not there is a reasonable possibility that the product under investigation caused or contributed to an adverse event.

Causality may be assigned with one of the following two possibilities:

- No: Definitely not drug related.
- Yes: remotely, possibly, probably, or definitely related to the drug

If the investigator's final determination of causality is unknown, and the investigator does not know whether the event was caused by the investigational product, then the event will be considered "related to the investigational product" for the purposes of event reporting. If the investigator's assessment of causality is "unknown, but clearly not related to the investigational product," that fact must be clearly documented in the study records. In addition, if the investigator determines that a serious adverse event is associated with the trial procedures, the investigator must record such causal relationship in the source documents and Case Report Forms, as applicable, and report such assessment in accordance with the requirements for reporting serious adverse events, if applicable.

All Adverse Events judged by the investigator or sponsor to be "drug related" qualify as an Adverse Drug Reaction (ADR).

10 STATISTICAL CONSIDERATIONS AND ANALYTICAL PLAN. SAMPLE SIZE CALCULATION

A recent study with JR-051, the first agalsidase beta biosimilar to be approved in Japan, was conducted in 20 volunteers (10 per treatment group), based on the fact that previous studies with this molecule assumed the geometric mean of C_{max} and ABC_{0-24} with a value of 1.0 and a coefficient of variation of 0.15.

Therefore, with a power = 0.80, significance level $\alpha = 0.05$, and a limit for accepting bioequivalence where the 90% confidence interval of the AUC ratio (for AUC_{0-120h} and AUC_{0-24}) should be within the range of 0.80-1.25 9 volunteers per group are required for the study, estimating the possibility of 1 volunteer lost to follow-up per group, the sample size was calculated in 20 volunteers.

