4 STUDY DESIGN

Pharmacokinetics, biological activity and immunogenicity will be studied in 20 healthy volunteers starting with a single dose of 1 mg/kg/body weight after administration via intravenous infusion of one (1) dose of:

- Sanofi-Genzyme Fabrazyme®. (Reference Formulation, "R"), or
- Biosidus SA Agalsidase beta (Test Formulation, "T")

This study was conducted under an open, randomized, parallel-arm, balanced, and sequential design. As it is a sequential design, if the statistical analysis of the first 20 volunteers does not show bioequivalence, additional volunteers will be included until the similarity criterion is verified with adequate power.

For volunteers and clinical staff, the study is open. Laboratory determinations will be completed in a blinded fashion, with coded samples.

Below (Figure 1), a study visit scheme is presented:

[figure not shown]

Figure 1 Study Visit Scheme

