6.4 TREATMENT DURATION

Study duration will be approximately 56 days for each volunteer, assuming: 21 days for the screening period (Visit 1), 1 day for hospitalization and treatment (Visit 2), 4 telephone contacts (days 3, 7, 14 and 21 - Visit 3, 4, 5 and 6) and 1 day for the Final Visit (day 35 – End of study).

Each volunteer will receive only one study formulation (T or R) at visit II (Hospitalization).

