7.1.1 Comparative pharmacokinetic analysis between formulations

ABC_T/ABC_R : Ratio between the area under the curve of each test formulation and the area under the curve of the reference formulation.

For logarithmic transformation, the 90% confidence interval of the AUC ratio (for $ABC_{0-120\text{ h}}$ and $ABC_{0-\infty}$) should be within the range of 0.80-1.25.

$C_{max\ T}/C_{max\ R}$: Ratio between the C_{max} of each Test formulation and C_{max} of the Reference formulation. For logarithmic transformation, the 90% confidence interval of the C_{max} ratio should be first within the range 0.80-1.25 (80% to 125%). Considering the high intra-individual variability of this pharmacokinetic parameter, if a variability > 30% is confirmed, this interval for the C_{max} may be extended to 0.75-1.33 (75-133%).

The FDA assumes that the test product is considered bioequivalent to the reference product if the 90% confidence interval (CI) of the geometric mean ratio of AUC and C_{max} between the test product and the reference product fall within the range 80-125%, even though the application of such criterion to drugs with high variability is controversial and regulatory agencies as strict as the FDA use different criteria. In Argentina, renowned specialists such as R. Bolaños, MD and S. Giarcovich, MD have analyzed the current status of the bioequivalence in the world proposing the most appropriate study designs.

Globally, drugs with high intra-individual variability are considered to be those with a coefficient of variation (CV) greater than 30% in pharmacokinetic parameters such as C_{max} and AUC. Different strategies have been tested given the high variability issue and in order to meet the conventional bioequivalence principles (90% CI 80-125). One has been to significantly increase the number of volunteers, sometimes to an unfeasible number, although this procedure does not guarantee that the results will fall within that equivalence interval. In this regard, there are reference products with high variability that are not capable of demonstrating bioequivalence with themselves. Additionally, the increase in volunteers to minimize variability poses an ethical problem, since we expose a greater number of healthy individuals to drugs that involve a risk in order to meet the bioequivalence criteria, which have been arbitrarily established. Other approaches have additional problems.

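### Section 10 plans Cmax on a CV of 0.15, while section 7.1.1 justifies wider Cmax limits by a within-subject CV above 30%; the two premises are incompatible, and the 0.80 power cannot stand for Cmax under the second

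*Combined protocol and SAP*

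**What the plan says.** Section 10 takes its planning values from a biosimilar study in 20 volunteers, 10 per group. That study relied on earlier work which assumed a geometric mean for Cmax and AUC "with a value of 1.0 and a coefficient of variation of 0.15". The calculation is stated "with a power = 0.80" and alpha 0.05, with "a limit for accepting bioequivalence where the 90% confidence interval of the AUC ratio" as its criterion, and it concludes that this "should be within the range of 0.80-1.25 9 volunteers per group are required for the study". One loss per group is added, giving 20 volunteers. No other CV is considered and no power is given for one.

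Section 4 describes an "open, randomized, parallel-arm, balanced, and sequential design", and section 6.4 confirms the single exposure: "Each volunteer will receive only one study formulation (T or R) at visit II".

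Section 7.1.1 requires Cmax to meet 0.80-1.25 first and then continues: "Considering the high intra-individual variability of this pharmacokinetic parameter, if a variability > 30% is confirmed", the interval may be extended to 0.75-1.33. The same section defines high intra-individual variability as a CV greater than 30%. It argues against meeting that problem with many more volunteers and says that extension of the limits is the approach used here for Cmax. AUC stays at 80-125%.

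**The concern.** The plan carries two premises about the variability of Cmax. Section 10 needs a CV of 0.15. Section 7.1.1 needs high variability as its reason for wider limits, and by its own definition high means more than 30%. No section reconciles them.

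At stake is what the 0.80 means. It is the only power figure in the plan, yet the acceptance criteria cover Cmax as well as AUC. If the variability that section 7.1.1 uses as its argument is real, a reader who takes 0.80 as the chance that Cmax passes in the first 20 volunteers is badly misled. The likelihood of having to expose further healthy volunteers is understated too, which is a burden section 7.1.1 itself raises. If 0.15 is right, the stated reason for wider Cmax limits falls away.

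**Working it through.** **Which CV drives power.** Each volunteer receives one formulation once, so the comparison is between different people. The variance of a log-transformed value is then the within-subject plus the between-subject variance. The total CV therefore cannot be below the within-subject CV, and a total of 0.15 cannot coexist with a within-subject CV above 0.30.

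**Inputs.** Ratio 1.0, CV 0.15, alpha 0.05 per one-sided test (90% CI), limits 0.80-1.25, and 9 or 10 per group (section 10); widened limits 0.75-1.33 and the 30% threshold (section 7.1.1).

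**Formula.** Two one-sided tests on the log scale: s = sqrt(ln(1 + CV²)), SE = s × sqrt(2/n), df = 2n − 2. With L and U the log limits, δ the log ratio, and q the estimated SD divided by s (df × q² is chi-square with df degrees of freedom), power is the mean over q of max{0, Φ((U − δ)/SE − t·q) − Φ((L − δ)/SE + t·q)}.

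**The plan's own figure.** At CV 0.15, s = sqrt(ln 1.0225) = 0.149. Power is 0.769 at 8 per group, 0.836 at 9 and 0.884 at 10. Nine is the smallest group size that reaches 0.80, so section 10 reproduces exactly. The match also confirms that 0.15 was used as a parallel-group CV.

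**Other CVs**, ratio 1.0, 9 / 10 per group:

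| Total CV | Limits 0.80-1.25 | Limits 0.75-1.33 |
|---|---|---|
| 0.15 | 0.836 / 0.884 | 0.975 / 0.987 |
| 0.20 | 0.481 / 0.564 | 0.803 / 0.857 |
| 0.25 | 0.193 / 0.256 | 0.527 / 0.609 |
| 0.30 | 0.059 / 0.085 | 0.280 / 0.356 |

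A simulation of 400,000 trials at CV 0.30 gives 0.059 / 0.085 and 0.281 / 0.357.

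**Why the last row is so low.** At CV 0.30, s = sqrt(ln 1.09) = 0.294. With 9 per group, SE = 0.294 × sqrt(2/9) = 0.138, and the typical CI half-width is 1.746 × 0.138 = 0.242. With 10 per group it is 1.734 × 0.131 = 0.228. Both exceed ln 1.25 = 0.223, so even an interval centred on a ratio of 1.0 would usually not fit.

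**Largest total CV that keeps power at 0.80.** Limits 0.80-1.25: 0.156 (9 per group) or 0.165 (10 per group). Limits 0.75-1.33: 0.201 or 0.213.

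**Why the figures at 0.30 are upper bounds under section 7.1.1's premise.**
- If 0.30 is only the within-subject part and a between-subject CV of 0.15 is assumed as well, the total is sqrt(1.09 × 1.0225 − 1) = 0.338. Power becomes 0.022-0.032, or 0.15-0.21 with the wider limits.
- With a true ratio of 0.95 and total CV 0.30, power is 0.055-0.079, or 0.26-0.33.
- The widened-limit column treats those limits as always available, whereas section 7.1.1 allows them only once variability above 30% is confirmed.

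**The case against.** The best defence is that section 7.1.1 describes a contingency. Cmax must meet 0.80-1.25 first, the extension depends on confirming more than 30%, and no section gives 30% as the expected CV for agalsidase beta. Planning on 0.15 while providing for something worse is legitimate. The remark on high variability can also be read as describing Cmax as a metric, since the section explains it by Cmax resting on a single measured point. This stands in part. The trigger is conditional, and power at CV 0.30 is power under the premise of section 7.1.1, not a forecast. But the clause before the trigger asserts high variability as a fact and uses it to justify the rule, so the premise still needs to be reconciled with 0.15.

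Three stronger readings are tempting, and the documents do not support them:
- A reader might infer an arithmetic error in section 10. There is none.
- A reader might infer that the 0.80 fails altogether. Section 10 ties its acceptance limit to AUC, and section 7.1.1 applies its high-variability premise to Cmax and keeps 80-125% for AUC. The AUC claim is not contradicted.
- A reader might infer that the whole trial has 6-9% power. Those figures concern Cmax in the first 20 volunteers. The design is sequential, and sections 4 and 5.1 allow more volunteers. No size or rule is given for that extension, so its effect on power cannot be computed, but it cannot be ignored either.

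**Conclusion.** The point holds for Cmax. The CV that section 10 plans on and the premise by which section 7.1.1 justifies wider limits are incompatible in this design. The 0.80 is sound for AUC at the assumed CV of 0.15. It is also sound for Cmax if the total CV is no more than about 0.155 (9 per group) or 0.165 (10 per group). Under the premise of section 7.1.1 it is not: first-stage Cmax power is at most 0.06-0.09, and widening the limits raises it only to 0.28-0.36. A CV well short of 30% already matters, because at 0.20 and the standard limits power is 0.48-0.56.

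This rests on a true ratio of 1.0, log-normal data, and reading the planning CV as the total CV. Section 10 does not use that word, but the design requires it and the reproduced 9 per group supports it.

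**What to change.** No change to the number of volunteers is asked for.

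- Section 10: state that the 0.80 applies to AUC, and to Cmax only if its total CV is no more than about 0.155 with 9 per group or 0.165 with 10. Add first-stage Cmax power for total CV 0.15-0.30 under both sets of limits; the table above can serve.
- Section 7.1.1: if 0.15 is kept for Cmax, remove the assertion that Cmax is highly variable. If the assertion is kept, withdraw the 0.80 claim for Cmax in the first 20 volunteers and give the lower figure.
- If the cited 20-volunteer biosimilar study reports an observed total CV, use it in place of the assumed 0.15. The documents do not show whether it does.

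The cost is wording in two sections and one small table. The downside for the sponsor is that the stated Cmax power may become less favourable.
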